Early Gestational Diabetes Screening in Gravid Obese Women

(EGGO)

Protocol

(Version 1.1; 02.17.2014)

Study Procedures

1. **Screening.** Records of health clinic patients will be reviewed by trained research staff to identify eligible patients. Eligible patients will receive a letter and/or phone call notifying them of their eligibility and asking them to participate. Trained research staff will be available at the OB Complications clinic and ultrasound to **screen** and **consent** patients. A screening log or form will be used to track all patients approached for the study. Women will be randomized at the time of consent. At the time of consent, women will sign a maternal/infant medical record release which will be faxed to any hospitals to obtain records for review if necessary.
2. **Randomization.** A confidential, computer-generated simple randomization scheme will be prepared by a designated study biostatistician. Randomization will be stratified by morbid obesity (BMI>40.0). Women will be randomized after they give consent by pulling the next sequential envelope from the participant's BMI group that will disclose whether the participant is assigned to early or routine timing of the GDM screen.
3. **Gestational Diabetes Screening.**
 - a. **Early Screening Group.**
 - i. Women assigned to "early screening" will complete the BSST (50-g glucose load) between 14 weeks, 0 days gestation and 20 weeks, 0 days gestation. If the test cannot be completed due to nausea or vomiting, the patient may choose to re-schedule another attempt prior to 20 weeks, 0 days or she may choose to withdraw from the study.
 1. If a participant is between 14 weeks, 0 days and 20 weeks, 0 days at the time of randomization she may:
 1. Choose to undergo BSST at the time of randomization in OBCC clinic. Add EGGO to her problem list with a message that she was randomized to early screening & the date of completion of the BSST.
 2. Choose to undergo BSST at next appointment at her local clinic. If she chooses this option, place a message in IMPACT and EGGO to her problem list with her randomization group. This will notify her provider to complete the BSST at the next visit prior to 18 weeks.
 - ii. At the time of the BSST, a purple and gold top tube will be drawn for HbA1c & Glycomark (refer to baseline procedures below). These specimens will be labeled with the patient name plate and sent to the OBGYN lab for testing.
 - iii. In those who are not diagnosed with GDM at the early screen, repeat testing will be performed at 24-28 weeks.
 - b. **Routine Screening Group.**
 - i. Women assigned to routine screening will have a blood draw for HbA1c and Glycomark between 14 weeks, 0 days and 20 weeks, 0 days gestation.

- If HbA1c $\geq 6.3\%$ in the routine screening group, the result will be unblinded and the clinician informed. These women will subsequently enter into routine GDM care with dietary counseling and patterned blood sugars.
 - If the patient is between 14 weeks, 0 days and 20 weeks, 0 days this blood draw may be performed at the enrollment visit. Otherwise, may be done in clinic with routine prenatal labs.
- ii. Women assigned to “routine screening” will undergo the 1-hour, 50-g glucose load (BSST) between 24 weeks, 0 days and 28 weeks, 0 days gestation. At the time of the BSST, a purple & gold top tube for HbA1c & Glycomark will be drawn (see baseline procedures below).

4. Results of Glucose screening tests

- a. Women whose BSST is ≥ 135 mg/dL, will be scheduled to undergo diagnostic testing with a 3-hour GTT (100-g glucose load). The currently used criteria to diagnose GDM (Carpenter Coustan criteria) will be used to diagnose GDM. By these criteria, a woman must have 2 elevated blood sugar values at either of the following timepoints and values:
1. Fasting ≥ 95 mg/dL
 2. 1-hour ≥ 180 mg/dL
 3. 2-hour ≥ 155 mg/dL
 4. 3-hour ≥ 140 mg/dL
- b. The attending physician will review the three-hour GTT results to confirm the diagnosis of GDM.
- c. Women who have a BSST > 200 will have a fasting blood sugar checked prior to undergoing a 3-hour GTT. If the fasting blood sugar < 126 mg/dL, the patient will proceed with a 3-hour GTT. If the fasting blood sugar ≥ 126 mg/dL, the diagnosis of GDM will be made.
- d. Women who are not diagnosed with GDM between 14-20 weeks (i.e. women who have a normal 1-hour BSST or who have an elevated 1-hour BSST but a normal 3-hour GTT) will repeat the 1-hour BSST at 24-28 weeks. At the time of the repeat BSST, a purple & red top tube for HbA1c & Glycomark will be drawn (see baseline procedures below).
- i. Women who are diagnosed with GDM will enter into routine GDM care with dietary counseling and patterned blood sugars. A purple & gold top tube for HbA1c & Glycomark will be drawn between 24-28 weeks, and 0 days gestation (see baseline procedures below).

- ii. Women who are not diagnosed with GDM (i.e. women who have a normal 1-hour BSST or who have an elevated 1-hour BSST but a normal 3-hour GTT) will continue routine prenatal care.
- iii. Women who are diagnosed with GDM will enter into routine GDM care with dietary counseling and patterned blood sugars.

5. Baseline Procedures

- Measurement of height, without shoes, at time of enrollment.
- Record self-reported prepregnancy weight.
- All women will have a blood draw for HbA1c and Glycomark between 14 weeks, 0 days and 20 weeks, 0 days gestation. The blood for HbA1c should be collected in a purple top tube (3mL). The blood for Glycomark should be collected in a gold top tube (3mL).
 - Women undergoing early GDM screening may have these blood samples drawn at the time of the blood draw for the 1-hour BSST.
 - Women randomized to routine screening may have these blood samples drawn at the time of randomization if between 14 weeks, 0 days and 20 week, 0 days. Otherwise, they may have the blood drawn at their clinic at an appropriate time (i.e. at the time of other routine prenatal lab draws).
 - Samples will be labeled with patient name plate for transport to OBGYN lab.
 - Samples may be stored at room temperature or 4°C (refrigerated) for up to 7 days.
- All women will have a blood draw for HbA1c and Glycomark between 24 weeks, 0 days and 28 weeks, 0 days gestation. The blood for HbA1c should be collected in a purple top tube (3mL). The blood for Glycomark should be collected in a gold top tube (3mL).
 - This blood draw may be performed at the time of the 1-hour BSST.
 - Women diagnosed with GDM prior to 24-28 weeks may have the blood drawn in clinic at the appropriate gestational age, in conjunction with routine prenatal lab draws or separately.
 - Samples will be labeled with patient name plate for transport to OBGYN lab.
 - Samples may be stored at room temperature or 4°C (refrigerated) for up to 7 days.
- Trained and experienced research staff in obstetric and perinatal outcomes abstraction will be responsible for all research data abstraction from patient medical records.
- Maternal outcomes will be ascertained in the hospital following delivery and at the routinely scheduled follow-up visit at 4-6 weeks after delivery.
- Newborn outcomes will be ascertained until 6 weeks after delivery through maternal questioning regarding re-admission. Readmissions for infants will be validated through medical review.

6. Follow-up

- a. Women with gestational diabetes will be contacted prior to their appointment by either phone or letter to remind them to come to their post-partum visit prepared for the fasting, 2-hour, 75-g glucose tolerance test.
- b. Women diagnosed with gestational diabetes will undergo a 2-hour, 75-g glucose tolerance test at the time of their post-partum visit at OBCC or resident continuity clinic. They will receive \$10 for undergoing this testing.
- c. All women will be asked whether they or their infant have been re-admitted to the hospital since the time of discharge and the reason for admission. Permission will be obtained to request records for re-admission diagnoses.

7. Outcome Measures

The primary outcome will be a composite outcome of macrosomia (birth weight >4000g), primary cesarean, gestational hypertension or preeclampsia, shoulder dystocia, neonatal hyperbilirubinemia, and neonatal hypoglycemia. Each of these outcomes will also be evaluated individually as secondary outcomes. Additional secondary outcomes will include premature delivery (<37wks).

- a. Macrosomia: Will be defined by measurement of infant birth weight. Macrosomia is a birth weight >4000 g.
- b. Primary cesarean: A primary cesarean delivery for any indication will be considered as having the outcome of interest.
- c. Gestational hypertension: Defined by systolic blood pressure ≥ 140 or diastolic blood pressure ≥ 90 without proteinuria (urine protein/creatinine ratio < 0.19 or 24-hour urine protein < 300 mg).
- d. Preeclampsia: Defined by systolic blood pressure ≥ 140 or diastolic blood pressure ≥ 90 with proteinuria (urine protein/creatinine ratio ≥ 0.19 or 24-hour urine protein ≥ 300 mg). Preeclampsia diagnosis will also be refined by mild or severe. Severe preeclampsia will be defined as systolic blood pressure ≥ 160 , diastolic blood pressure ≥ 110 , proteinuria ≥ 5000 mg in 24 hours or 3+ urine dip, platelets < 150 , AST > 60 , oliguria (< 500 mL urine/ 24 hours), pulmonary edema, creatinine > 1.0 .
- e. Shoulder dystocia: As documented by delivering physician; defined as requiring more than routine downward traction to achieve delivery of anterior shoulder. The length of the shoulder dystocia and maneuvers required to relieve the shoulder dystocia will be documented.
- f. Neonatal hyperbilirubinemia: Neonatal bilirubin levels will be recorded. Hyperbilirubinemia will be defined $> 95^{\text{th}}$ percentile gestational age and hour of life. The treatment of hyperbilirubinemia (i.e. phototherapy) will also be recorded.
- g. Neonatal hypoglycemia. Blood sugar levels will be abstracted from neonatal charts. Neonatal hypoglycemia will be defined as blood sugar < 35 mg/dL.

8. Data Collection Form Definitions

- a. Randomization Form
 - i. Age at the time of presentation
 - ii. Body mass index as defined by self-reported pre-pregnancy weight & measured height
 - iii. Gestational age <20 weeks, 0 days as defined by earliest documented ultrasound
 - iv. Known history of diabetes mellitus by patient report or as documented in clinical records
 - v. Major medical illness
 - 1. Chronic/daily prednisone use
 - 2. On home oxygen
 - 3. Prior cardiac surgery
 - 4. History of cardiomyopathy, valvular stenosis, pulmonary hypertension
 - 5. History of any transplanted organ
 - 6. HIV/AIDS
 - 7. Hemoglobinopathy (i.e. sickle cell disease)

Conditions not considered a major medical illness:

 - 1. Chronic hypertension
 - 2. Asthma (unless requiring prednisone on daily basis)
 - 3. Obstructive sleep apnea (unless requiring home oxygen)
 - vi. Unable to provide informed consent
 - 1. Language barrier
 - 2. Prisoner
 - 3. Mental illness
 - 4. Judgment of person performing enrollment
 - vii. Known fetal anomalies
 - 1. Structural anomalies (heart defect, brain defect, renal anomaly, abdominal wall defect) or known fetal aneuploidy by karyotype or non-invasive prenatal diagnosis
 - 2. Soft markers of aneuploidy are not exclusion criteria (echogenic intracardiac focus, choroid plexus cyst, renal pelvis dilation/pyelectasis)
 - viii. History of bariatric surgery
 - 1. Either banding procedure or Roux-en-Y
 - ix. Multifetal gestation
 - x. Prior cesarean
- b. Enrollment Form
 - i. Measured height without shoes

- ii. Self-reported pregnancy weight obtained from patient interview at time of enrollment
 - iii. History may be obtained from patient directly or from chart
 - iv. Exam at time of enrollment
- c. Diabetes Testing Form
 - i. Document Randomization group
 - ii. Document date and value of BSST, GTT, HbA1c, and Glycomark
- d. Prenatal Care Data Collection Form
 - i. Document whether exclusion criteria developed during course of prenatal care
 - ii. Record number of prenatal visits and date, weight, and blood pressure each visit.
 - iii. Document date, indication, estimated fetal weight, and amniotic fluid index of each ultrasound.
 - iv. Document date and type of antenatal testing performed, & indication for test.
 - v. Document all medications prescribed for gestational diabetes. Date started, the starting dose & frequency, the stop date, and the highest dose reached.
 - vi. Review other medications and document that there are no changes in medications or update medication list
- e. Blood Sugar logs
 - i. Record blood sugar logs patient provided. Date, fasting blood sugar, post-prandial blood sugar after each meal, and 21:00 & 3:00 AM blood sugar if documented.
- f. Delivery Data Collection Form
 - i. Date of admission
 - ii. Admitting diagnosis as documented by admitting physician history & physical
 - iii. Admission vital signs and labs as documented by the first vital signs and labs obtained on day of admission
 - iv. Gestational diabetes type
 - v. Blood sugar log & insulin drip as per IMPACT records
 - vi. Type of labor as documented by admitting physician history and physical
 - vii. Indication for induction of labor based on documentation by admitting physician history & physical
 - viii. Indication for scheduled cesarean as documented by admitting physician history & physical
 - ix. Medications received during labor: Check all that apply. Any medication received between the time of admission and delivery should be checked.
 - x. Record the mode of delivery, indication for operative delivery, shoulder dystocia, laceration/episiotomy, as documented by physician labor and delivery note. If information not documented by physician labor and delivery note, use nursing notes to complete information.

- xii. Post-partum hematocrit – Either spun hematocrit or hematocrit from CBC at 12 hours post-delivery.
- xiii. Endometritis as documented by caring physician.
- g. Neonatal Form
 - i. Highest level of neonatal resuscitation in delivery room as documented by caring pediatricians
 - ii. Admitting diagnosis for infant to nursery as documented by pediatricians admission note
 - iii. Cause of death as documented by expiration summary
 - iv. Neonatal injuries as documented by pediatrics admission note & daily notes prior to discharge
 - v. Method of feeding as documented by nursing notes/pediatricians notes
- h. Post Partum
 - i. Readmission of mother to hospital after initial discharge – obtain by questioning mother and obtain confirmation with records request
 - ii. Readmission of infant to hospital after initial discharge – obtain by questioning mother and obtain confirmation with records request

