**3.1.2. Analysis Plan:** This hypothesis effect of Early versus Routine GDM screening in obese pregnant women. The  $\chi^2$  test of association will be used to evaluate whether the rate of the primary outcome differs between the treatment groups. The primary analysis will be an intention-to-treat analysis of all individuals randomized to the two treatment groups, regardless of whether evaluation plans were followed. Risk ratios (RR) and 95% confidence intervals (CIs) will be computed and presented.

Standard comparison of the covariate characteristics at baseline between study groups will be undertaken (Section 2) to assess the randomization balance on measured covariates. Tests of significance will be two-sided and evaluated at the 0.05 level of significance. Since the sample size for EGGO is large, it is unlikely that “important” covariates (such as race, BMI or age) will be imbalanced through the

randomization process. Further, randomization is stratified by BMI (BMI <40 and BMI ≥40) and site (UAB and Oschsner).

In the unlikely event that imbalance occurs, adjustment for covariates will be made by modeling the log-odds of the outcome using multivariable logistic regression including terms indicating group membership and each of the imbalanced covariates. In other words, the log-odds of the primary outcome for any individual will be modeled using the following form:

$$\ln\left(\frac{P(\text{outcome})}{1-P(\text{outcome})}\right) = \beta_0 + \beta_1 x_1 + \sum \beta_j z_j.$$

Above,  $x_1 = 1$  if the patient is in the Early group and equals 0 if the patient is in the Routine group. The set of  $z_j$ 's consists of all covariates in the model including site. Hence, under this model, the term  $\beta_1$  represents the difference in the log-odds between the two groups. To address the hypothesis of interest for primary hypothesis #1, we will perform a statistical test of  $H_0: \beta_1 = 0$  vs.  $H_1: \beta_1 \neq 0$ . Quantification of the treatment effect will be performed by exponentiation of the estimated coefficient,  $\exp(\beta_1)$ , to obtain an estimate of the odds ratio. The confidence interval will be determined similarly.

The stratification by BMI and by site allows for the investigation of differential effects across sites and across BMI thresholds. The presence of a homogeneous effect across center and across BMI thresholds will be examined using the Breslow-Day test.

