**3.1.3. Sample Size for Primary Outcome:** Based on prior studies performed at UAB, the incidence of macrosomia, cesarean delivery, shoulder dystocia, and preeclampsia in obese women with gestational diabetes was 56%. Using a conservative estimate of these outcomes as 50%, to detect a 50% reduction in the incidence of adverse outcomes ( $\alpha=0.05$ ,  $\beta=0.80$ ), 58 gestational diabetics per group are necessary.

The diagnosis of GDM will occur after patients in this study have been screened for GDM. As a result, a large number of patients must be randomized to each diagnostic procedure in order to achieve 58 gestational diabetics in each group. Prior reports of the incidence of GDM are between 6-20% depending on ethnicity and the screening and diagnostic criteria used. Using an incidence of 10% GDM in obese women, 580 subjects per screening group are necessary. Approximately 3,100 women per year attend the UAB clinic for obstetric visits, and approximately 40% of these women are obese. Assuming a 50% acceptance of enrollment, we anticipate enrolling 620 women per year. Therefore, we feel that we can enroll 1,160 subjects in 3 years.

**3.2. Interim Monitoring:** One interim analysis, evaluating both efficacy and futility, will be conducted after 600 women have completed the study (300 in each group have delivered). Under the assumption that 10% of obese women have GDM, we expect to have approximately 30 gestational diabetics in each group. Using an O'Brien-Fleming alpha spending function and one interim analysis, we will use the following critical stopping values:

At the interim look:     If  $\chi^2 > 7.82$  (i.e.  $p < 0.005$ ) then reject  $H_0$  and consider stopping the trial;  
                                  Otherwise, continue.

At the final look:        If  $\chi^2 > 3.91$  (i.e.  $p < 0.048$ ) then reject  $H_0$ .

We do not propose a formal stopping rule for safety or futility, but note that the DSMB will be presented with safety data and information on study progress. In addition, we note that the overall sample size of 58 gestational diabetics per group will provide 80% power for the hypothesized effect size using a modified alpha level of 0.048 at the final analysis. Conditional power estimates may be provided to assist the DSMB in their evaluation of efficacy and futility.

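### The sample size allows for no loss after randomization, although women are randomized at consent, some before 14 weeks when the arms cannot yet differ

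*Protocol*

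**What the plan says.** **Time of randomization.** Protocol section 1 (Screening) states "Women will be randomized at the time of consent". The Randomization Form definitions (Protocol 8.a.iii) give the gestational criterion as "Gestational age <20 weeks, 0 days as defined by earliest documented ultrasound". No lower limit appears.

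**Entry before 14 weeks is foreseen.** In the Early arm, Protocol 3.a.i treats being in the window already as a conditional case: "If a participant is between 14 weeks, 0 days and 20 weeks, 0 days at the time of randomization she may". For the Routine arm, Protocol section 5 (Baseline Procedures) adds a route for women not in the window at randomization: "Otherwise, they may have the blood drawn at their clinic at an appropriate time". Entry closes at 20w0d, so that route serves women who have not yet reached 14w0d.

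**First difference between arms.** Women in the Early arm "will complete the BSST (50-g glucose load) between 14 weeks, 0 days gestation and 20 weeks, 0 days gestation" (Protocol 3.a.i). The HbA1c and Glycomark sample in the same window is common to both arms: "All women will have a blood draw for HbA1c and Glycomark between 14 weeks, 0 days and 20 weeks, 0 days gestation" (Protocol section 5).

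**Losses the protocol provides for.** An Early-arm woman who cannot complete the BSST because of nausea or vomiting may withdraw (Protocol 3.a.i). Exclusion criteria that arise during prenatal care are recorded (Protocol 8.d.i).

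**Analysis set and sample size.** The primary analysis is an "intention-to-treat analysis of all individuals randomized to the two treatment groups" (SAP 3.1.2). SAP 3.1.3 requires 58 women with GDM per group and continues: "Using an incidence of 10% GDM in obese women, 580 subjects per screening group are necessary". SAP 3.2 repeats the 80% power claim for 58 per group at a final alpha of 0.048. No allowance for pregnancy loss, withdrawal or missing outcomes is given.

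**The concern.** The number to randomize is the number of women with GDM divided by the GDM incidence, and nothing more. That holds only if every randomized woman reaches GDM testing and has her outcome assessed. Randomizing at consent makes this harder to meet, because a woman who enters before 14w0d has a period in which her pregnancy can end, or she can leave, before the two strategies differ at all. She remains in the set of all randomized women but can tell us nothing about the timing of screening.

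At stake are the expected number of women with GDM and the power figure that SAP 3.1.3 and 3.2 rely on. Early losses also blur the contrast between arms, because they are randomized women to whom the comparison could not apply.

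**Working it through.** **Inputs from the SAP.** Event rate among women with GDM 50%, to be halved to 25%; two-sided alpha 0.05, and 0.048 at the final look; power 80%; 58 women with GDM per arm; GDM incidence 10%; 580 per arm, 1,160 in total (SAP 3.1.2, 3.1.3, 3.2).

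**Input not in the documents.** The loss fraction d, meaning loss from any cause between randomization and outcome. It is assumed here at 2%, 5% and 10%.

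**Step 1: reproduce the 58.** Two proportions, pooled variance under the null, no continuity correction, mean proportion p = (0.50 + 0.25)/2 = 0.375:

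n = [z(α/2)·√(2p(1−p)) + z(β)·√(p1(1−p1) + p2(1−p2))]² / (p1 − p2)²

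= [1.960·√0.46875 + 0.8416·√0.4375]² / 0.0625 = 57.7, rounded up to 58. This matches the SAP.

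**Step 2: reproduce the 580.** 58/0.10 = 580, and 2 × 580 = 1,160. Both match exactly, so the implied loss is 0%.

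**Step 3: power with no loss.** Power = Φ{[0.25·√n − z(α/2)·√0.46875] / √0.4375}. At n = 58 this is 80.2% for alpha 0.05. For alpha 0.048, z = 1.977 and the argument is (1.904 − 1.354)/0.661 = 0.832, so power is 79.7%. At alpha 0.048 the required n is 58.4, rounded up to 59. The plan therefore has no margin at its own final alpha.

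**Step 4: apply loss with 1,160 randomized.** Women with GDM per arm = 580 × (1 − d) × 0.10.

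| Assumed loss d | Women lost of 1,160 | Women with GDM per arm | Power, alpha 0.05 | Power, alpha 0.048 |
|---|---|---|---|---|
| 0% | 0 | 58.0 | 80.2% | 79.7% |
| 2% | 23 | 56.8 | 79.4% | 78.9% |
| 5% | 58 | 55.1 | 78.1% | 77.6% |
| 10% | 116 | 52.2 | 75.9% | 75.3% |

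At alpha 0.048 the falls are 0.8, 2.1 and 4.4 percentage points.

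**Step 5: scale of the missing allowance.** Keeping 58 would take 580/(1 − d) per arm: 592, 611 or 645. These figures show the size of the gap and are not a proposal to enlarge the trial.

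**Step 6: how much of d can arise before 14 weeks.** That part of d is the share of women randomized before 14w0d multiplied by the fraction of them lost before 14w0d. The documents give neither. If 30% entered that early (an assumption), a 5% overall loss from this source alone would need 5/30 = 17% of them to be lost, and a 10% loss would need 10/30 = 33%. The larger values of d therefore have to be read as loss at any stage.

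**The case against.** **The effect is small and other uncertainties are larger.** This stands as to size. SAP 3.1.3 calls 50% conservative against an observed 56%. If the rates were 56% and 28%, 52.2 women per arm would still give 83% power at alpha 0.048. The SAP's own GDM range of 6% to 20% gives 35 to 116 women per arm (580 × 0.06 and 580 × 0.20), a far wider spread than 52 to 58. However, the SAP presents neither as a loss allowance, and its stated 80% still rests on 58.

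**A reader might infer that early randomization biases the comparison.** The documents do not support that. Pregnancy losses before the arms differ are balanced apart from chance. The envelope discloses the arm, so departure that depends on allocation is possible. But the only withdrawal route described follows a failed early BSST, which falls at or after 14w0d.

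**A reader might count every transfer or later exclusion as lost.** That goes too far. The records release signed at consent can recover outcomes after a transfer (Protocol section 1), and a woman who develops an exclusion still belongs in an intention-to-treat set. Early pregnancy loss and full withdrawal are the clear cases.

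**The power figures are not those of the planned test.** Correct. They are on the SAP's GDM-only basis, whereas the primary test uses all randomized women. They correct the SAP's stated figure and do not give the power of that test.

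**Randomizing at consent is practical.** It is: a message and a problem-list entry tell the local provider the arm in advance. This is why the later envelope is proposed only where feasible.

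**Conclusion.** The point holds in a limited form. SAP 3.1.3 assumes zero loss, while the protocol randomizes at consent, foresees entry before 14w0d and provides for withdrawal and later exclusions. With 1,160 randomized, any loss takes the expected number of women with GDM below 58 per arm. The cost is modest: about 2 points of power at 5% loss and about 4 at 10%, from a start of 79.7%.

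This rests on assumed loss rates, on the SAP's 10% GDM incidence and 50% versus 25% event rates, and on the GDM-only basis. The documents do not show how much of any loss would fall before 14w0d, so the figures cannot be attributed to the timing of randomization alone.

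Two neighbouring matters are separate and are not settled here: withdrawal after a failed early BSST, which can occur only in the Early arm, and the mismatch between power computed in women with GDM and a test on all randomized women.

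**What to change.** 1. **SAP 3.1.3.** Keep 1,160. State the loss rate seen so far, pooled over arms, and restate the expected number of women with GDM per arm and the resulting power at alpha 0.048. Carry the revised figure into the 80% power statement in SAP 3.2. The cost is a short text revision.

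2. **Protocol sections 1 and 2.** Where feasible, for women who consent before 14w0d, open the envelope at or just after 14w0d, early enough in the window to leave time for the early BSST. Women lost before then are never randomized, and the analysis of all randomized women stays intact without post-randomization exclusions. Count accrual from the opening of the envelope.

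The cost of the second change is that some consented women are never randomized, accrual is slightly slower, and staff need a phone or message step for women seen at local clinics. It does not remove losses after 14w0d, so the first change is needed in any case.

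### An Early-arm woman who cannot complete the glucose load is offered study withdrawal, without the option of staying in outcome follow-up; the Routine arm has no such offer

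*Protocol*

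**What the plan says.** **Timing.** Protocol section 1 (Screening) states: "Women will be randomized at the time of consent". Any exit prompted by a glucose test therefore happens after randomization.

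**Early arm.** Protocol 3.a.i covers the 14-20 week test. When nausea or vomiting prevents completion, "the patient may choose to re-schedule another attempt prior to 20 weeks, 0 days or she may choose to withdraw from the study". Both courses are the woman's choice. Continuing untested in outcome follow-up is neither listed nor forbidden.

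**Routine arm.** Under Protocol 3.b.ii these women "will undergo the 1-hour, 50-g glucose load (BSST) between 24 weeks, 0 days and 28 weeks, 0 days gestation". Section 3.b does not mention an uncompleted test or withdrawal.

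**Analysis.** SAP 3.1.2 specifies an "intention-to-treat analysis of all individuals randomized to the two treatment groups, regardless of whether evaluation plans were followed".

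**Outcome collection.** None of it depends on the glucose test. At consent, "women will sign a maternal/infant medical record release" (Protocol section 1). Trained research staff "will be responsible for all research data abstraction from patient medical records" (section 5). Section 5 also says: "Maternal outcomes will be ascertained in the hospital following delivery and at the routinely scheduled follow-up visit at 4-6 weeks after delivery". The prenatal form in 8.d.ii has staff "Record number of prenatal visits and date, weight, and blood pressure each visit".

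**The concern.** The wording in 3.a.i merges two different events: not completing a screening test, and leaving the study. In a trial of screening strategies, the first is ordinary non-adherence, which an intention-to-treat analysis is meant to absorb. The second can remove the woman's primary outcome.

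The prompt is attached only to the 14-20 week load, which only the Early arm receives. It is triggered by a patient characteristic, nausea and vomiting in pregnancy, that may be related to outcome. If women take the offer and their outcomes are not obtained, the loss is post-randomization, tied to one arm and possibly selective. The intention-to-treat sentence says who belongs in the analysis. It does not supply their data.

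Such loss would be largely avoidable, because the record release and chart abstraction work equally well for a woman who never drank the glucose.

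**Working it through.** **The plan's own numbers.** SAP 3.1.3 assumes 50% versus 25% in women with GDM, alpha 0.05 and 80% power. The pooled-variance two-proportion formula without continuity correction is

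n = [1.960 × √(2 × 0.375 × 0.625) + 0.842 × √(0.5 × 0.5 + 0.25 × 0.75)]² / 0.25² = 57.7, rounded up to 58 per group.

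Then 58 / 0.10 = 580 per group, and 2 × 580 = 1,160. The plan's figures are reproduced, and they contain no allowance for loss.

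**Inputs for the bias calculation.**
- From the SAP: 580 women per arm; two-sided final alpha 0.048.
- Assumed, because neither document gives them: composite rate in all women p = 0.45 (range 0.35 to 0.55); share of the Early arm lost w = 2% or 5% (about 12 or 29 women); relative risk of the composite in those lost k = 0.7 to 1.5; no such loss in the Routine arm; no true treatment effect; complete-case analysis.

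**Shift in the observed Early-arm rate.** The women who remain have rate p(1 - wk)/(1 - w), so

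shift = p × w × (1 - k) / (1 - w).

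Example, p = 0.45, w = 0.05, k = 1.5: 0.45 × 0.05 × (-0.5) / 0.95 = -1.18 points.

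| p | w | k = 0.7 | k = 1.0 | k = 1.5 |
|---|---|---|---|---|
| 0.35 | 2% | +0.21 | 0 | -0.36 |
| 0.35 | 5% | +0.55 | 0 | -0.92 |
| 0.45 | 2% | +0.28 | 0 | -0.46 |
| 0.45 | 5% | +0.71 | 0 | -1.18 |
| 0.55 | 2% | +0.34 | 0 | -0.56 |
| 0.55 | 5% | +0.87 | 0 | -1.45 |

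(percentage points)

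**Against sampling error.** With full data the standard error of the difference is √(2 × 0.45 × 0.55 / 580) = 2.92 points. After the loss it is 2.94 points at 2% and 2.96 at 5%. At p = 0.45 the largest shifts are 0.46 / 2.94 = 0.16 and 1.18 / 2.96 = 0.40 standard errors.

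**Type I error.** The critical value for two-sided 0.048 is 1.977. With a shift of d standard errors, the rejection probability under no effect is close to Φ(-1.977 + d) + Φ(-1.977 - d). At p = 0.45:
- 2% loss: 0.049 (k = 0.7), 0.051 (k = 1.5).
- 5% loss: 0.055 (k = 0.7), 0.066 (k = 1.5). The last rises to 0.075 if p = 0.55.

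**Loss needed for a 1-point shift.** w = 0.01 / (0.45 × |1 - k| + 0.01):
- k = 1.5: 0.01 / 0.235 = 4.3%, about 25 women.
- k = 0.7: 0.01 / 0.145 = 6.9%, about 40 women.

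**Precision and power.** The standard error grows by √((1/(1 - w) + 1)/2): 1.005 at 2% and 1.013 at 5%. On the SAP's own basis of women with GDM, Early-arm loss of 2% or 5% leaves 56.8 or 55.1 expected cases instead of 58. Power at alpha 0.048 goes from 79.7% to 79.3% or 78.6%. Both effects are trivial.

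**The case against.** The strongest case is that this is permissive drafting with little practical effect. The woman may choose; nothing requires her to leave, and nothing makes outcome collection depend on the test. The rest of the Protocol treats staying in as the default, and the SAP analyses her whatever happened to her test. She could withdraw without this sentence, and so could a Routine-arm woman. Most components of the composite are in hospital charts in any case, and the signed release may allow them to be used. The consent pages that would settle this are not in the material available. The upper figure of 0.066 needs 5% loss in one arm only, no record retrieval and a composite risk of 0.45 × 1.5 = 67.5% in the women lost. The Early arm's own repeat test at 24-28 weeks carries no such offer either.

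Much of this stands. The asymmetry lies in the offer attached to the early test, not in the right to withdraw. The bias is small under most assumptions and zero if the women lost have average risk. Since the consent pages are unseen, it cannot be said that a rule on record use after withdrawal is missing.

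What remains is that staff following 3.a.i see two choices, one of which can end outcome collection for a reason that has no bearing on whether outcomes can be collected. The SAP's analysis rule takes effect too late to repair that.

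**Conclusion.** The concern holds and should be addressed, as an inexpensive safeguard and not because serious bias has been shown. Protocol 3.a.i gives Early-arm women a test-triggered offer to leave the study after randomization. It does not list remaining in follow-up, and it has no Routine-arm counterpart. That is at odds with the purpose of the intention-to-treat analysis in SAP 3.1.2.

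The true size is unknown, since the documents give no intolerance or withdrawal rate. Under the stated assumptions the bias is negligible at 2% loss (at most 0.16 standard errors) and modest at 5% (at most 0.40). It takes roughly 25 to 40 women lost from one arm to move the observed rate by a full point. Confidence is medium, because the effect depends on how often the offer is taken and whether records may be used afterwards.

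**What to change.** **Protocol 3.a.i and 3.b.** Replace the withdrawal offer with the same text in both arms, for example:

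> A woman who does not complete the screening test remains in outcome follow-up. Her outcomes are abstracted from records as far as her consent allows, and she is analysed in her randomized group. Withdrawal from the study, which is open to any woman at any time, is recorded separately.

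**SAP 3.1.2.** Report test non-completion and study withdrawal by arm. If any composite outcomes are missing, add a simple sensitivity analysis, such as best-case and worst-case bounds.

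**Minor alignment.** Protocol 3.a.iii retests all women not diagnosed at the early screen, while the explanation in 4.d describes only women who have a test result. The two should be reconciled on whether women with no early result are included. Their clinical management is for the investigators.

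**Cost.** A short protocol amendment, one or two SAP sentences, and a check of the consent wording on record use after withdrawal. The right to withdraw is unchanged, and the abstraction staff and forms are already planned.
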